4.2 Design Diagram

This study is a Phase 3, multi-center, open-label study designed to evaluate the long-term maintenance of clinical response, safety and tolerability of ADA in pediatric subjects with ulcerative colitis.

Subjects are eligible to enroll in the Study M10-870 if they have successfully completed Protocol Study M11-290 through Week 52 and meet all of the inclusion criteria and none of the exclusion criteria for Study M10-870.

The Week 52 visit from the Study M11-290 serves as the Baseline Visit for subjects entering Study M10-870.

All subjects receive open-label therapy as follows beginning at the Baseline Visit in Study M10-870:

- Subjects who enroll into the study from blinded treatment in Study M11-290 receive open label 0.6 mg/kg (maximum of 40 mg) every other week (EOW) of adalimumab
- Subjects who received open label 0.6 mg/kg (maximum of 40 mg) every week (EW) of adalimumab in Study M11-290 maintain the same dose in Study M10-870

Subjects who demonstrate a disease flare may have their dose escalated. Subjects who have been in remission (PMS \leq 2 with no individual subscore > 1) for at least 8 weeks and for at least 2 consecutive visits may have their dosage de-escalated. Subjects who demonstrate disease flare after dose de-escalation have an opportunity to re escalate their dose back to adalimumab every week (EW) dosing.

[figure not shown]
Subjects with persistently uncontrolled disease while on adalimumab 40 mg EW (maximum dose) are to be discontinued from the study.

The duration of the study is up to 298 weeks (approximately 5.5 years).

More details are described in the protocol, including the Study Activities table.

4.3 Sample Size

Subjects who successfully completed Study M11-290 through Week 52 are potentially eligible to participate in this study. Originally, based on an expected number of 155 subjects being re-randomized at Week 8 of the parent study, an expected Study M11-290 completion rate of 66% and a roll-over rate of 80% of eligible subjects (based on previous experience with the pediatric CD Studies M06-806 and M06-807) it was expected that approximately 85 subjects from Study M11-290 would enroll into the

main Study M10-870 study and 8 subjects from the Japanese sub-study. However, as per Study M11-290 protocol Amendment 5 the parent study will be closed with N = 101 (N = 93 in main study + N = 8 in Japan sub-study) and the expected sample size in Study M10-870 is approximately 60 subjects (55 Ex-Japan and 5 in Japan).

4.4 Interim Analysis

An interim analysis on safety and efficacy will be performed and reported in a full Interim Clinical Study Report for inclusion of the Study M10-870 data in the submission of applications for regulatory approval of the pediatric UC indication in conjunction with the Study M11-290 results. Additional interim analyses may be performed, as needed.

5.0 Analysis Populations

5.1 Definition for Analysis Populations

[figure not shown]
The Full Analysis Set will be used for all analyses and includes all subjects who received at least one dose of ADA in Study M10-870.

6.0 Analysis Conventions

General Considerations

All statistical analysis results will be reported using descriptive statistics. Descriptive summary statistics will be provided for the demographic and Baseline characteristics, efficacy, and safety parameters.

Continuous variables will be summarized by sample size (N), mean, standard deviation, minimum, Q1, median, Q3, and maximum. Frequency and percentages will be provided for the categorical variables. For dichotomized efficacy variables, data will be summarized by number and percent of subjects with 95% confidence interval.

Week 0 and Baseline Visit Date

Week 0 is defined as the Week 52 visit from the Study M11-290. This date is also referred to as the baseline visit date.

Definition of Baseline Measurement

Unless otherwise notes, the baseline value for a variable is defined as the last non-missing value before the baseline visit date (i.e., at or before the Week 52 visit from the Study M11-290). In some instances Study M11-290-Baseline will be used, but this will always be specified accordingly.

[figure not shown]
Definition of Final Measurement

Final evaluation during the study: the last non-missing observation collected in the study after the first dose of study drug.

Final evaluation during ADA exposure in Study M10-870 (for laboratory analyses): the last non-missing observation collected in the study within the ADA exposure window in Study M10-870 (see Section 9.1).

Definition of Rx Days (Days Relative to the First Dose of Study Drug)

Rx Days are calculated for each time point relative to the date of first dose of study drug in Study M10-870. They are defined as the number of days between the day of the first dose of study drug and the specific time point. Rx Days are negative values when the time point of interest is prior to the first study drug dose day. Rx Days are positive values when the time point of interest is after the first study drug dose day. The day of the first dose of study drug is defined as Rx Day 1, while the day prior to the first study drug dose is defined as Rx Day –1 (there is no Rx Day 0).

[figure not shown]

Definition of Analysis Windows

All time points and corresponding time windows are defined based on Rx days. The protocol specified visits and corresponding time windows are presented in the table below. Measures will only be displayed at the visits where they were planned to be measured. For example, Mayo score is collected at Weeks 0, 48, 96, 192 and 288/Premature Discontinuation (dependent on availability of optional endoscopy data at these timepoints).

Assigned Visit	Nominal Day	Time Window (Rx Day Range)
Week 0	1	≤ 1
Week 4	29	2 to 43
Week 8	57	44 to 71
Week 12	85	71 to 127
Week 24	169	128 to 211
Week 36	253	212 to 295
Week 48	337	296 to 379
Week 60	421	380 to 463
Week 72	505	464 to 547
Week 84	589	548 to 631
Week 96	673	632 to 715
Week 108	757	716 to 799
Week 120	841	800 to 925
Week 144	1009	926 to 1093
Week 168	1177	1094 to 1261
Week 192	1345	1262 to 1429
Week 216	1513	1430 to 1597
Week 240	1681	1598 to 1765
Week 264	1849	1766 to 1933
Week 288	2017	1934 to 2101

If more than one assessment is included in a time window the assessment closest to the nominal day should be used. If there were more than one observation with equal distance to the nominal day the latest one will be used in analyses. For any given variable, if more

than one measurement exists for a subject on the same day, the average of the measurements will be considered to be that subject's measurement for that day.

Missing Data Handling

In general, missing Baseline and safety data will not be imputed.

Baseline Value is Missing:

Subjects will be excluded from analysis of change from Baseline if Baseline evaluation is missing.

Missing Efficacy and Outcome Evaluations:

The following methods will be used for imputing missing values to perform the efficacy analyses.

[figure not shown]
For interim analyses, missing values will only be imputed up to the timepoint a patient could have potentially reached at the data cutoff for analyses.

Observed Cases (OC): missing values will not be used for the observed case analysis.

Last Observation Carried Forward (LOCF): For categorical and continuous efficacy variables the following rules will be used for LOCF approach:

- Baseline and pre-baseline values will not be used to impute the missing post-baseline values, and
- Missing values after baseline will be imputed using the last non-missing values after baseline and prior to the missing value.

For composite scores which consist of several component subscores, components will be imputed first and the composite score will be calculated based on imputed component subscores. Only if composite score still can't be calculated after imputing component subscores, then the previous composite score will be carried forward.

[figure not shown]

Missing Items on Questionnaire Scales:

Mayo scores (and alternative composite scores) can only be calculated if all subscores included are collected. If one or more subscores are missing, the score will be considered missing. No imputations will be made. The symptoms of stool frequency and rectal bleeding are scored as a 5 day average of daily values from up to 14 days preceding the visit, rounded to one decimal place. The most recent consecutive days will be used. If consecutive days are not available, then non-consecutive days can be used. Diary entries for stool frequency and rectal bleeding should not be included in the 5 days prior to the visit that are evaluated for these subscores for the following days: (1) the day the subject received medication for bowel preparation prior to endoscopy, (2) the day the subject underwent an endoscopy, and (3) 2 days following the endoscopy. Earlier diary entries will be used accordingly in order to provide the most recent data for 5 days prior to the respective study visit. If less than 3 days of diary data are available, stool frequency and rectal bleeding subscores will be considered missing.

[figure not shown]
When calculating **PUCAI**, if more than 3 subscores are missing then PUCAI will be considered missing. Otherwise, for missing subscores, the last available post-baseline value for the respective subscore will be carried forward to compute the total PUCAI score. The subscores of abdominal pain, rectal bleeding, stool consistency, number of stools per 24 hours, nocturnal stools and activity level are scored as a 2 day average, rounded to one decimal place. The most recent consecutive days will be used. If consecutive days are not available, then non-consecutive days can be used.

When calculating **IMPACT III** total score, if 4 or more of the items are missing then IMPACT III total score and all subscores will be considered missing. Otherwise, if there are 3 or fewer missing answers, the average of non-missing values will be used to replace the missing items for the total score and subscore calculation. If for subscores consisting of only 3 items (see 'Score Definitions' later in this Section), all of these items are missing and are replaced per above convention, a footnote will be added indicating for how many subjects the subscore included in the analysis has been fully imputed.

When calculating the **WPAI** scores, the following computational notes should be followed.

- Define Employment as a binary YES or NO variable where YES corresponds to "Employed" and NO corresponds to "Not Employed":
 - A subject will be considered EMPLOYED at a given visit if Q1 = YES or Q2 > 0 or Q4 > 0.
 - A subject will be considered UNEMPLOYED at a given visit if Q1 = NO and no positive hours recorded under Q2 and Q4 (i.e., if Q1 = NO AND $Q2 \le 0$ AND $Q4 \le 0$, then UNEMPLOYED).
 - Employment status for a subject will be considered missing at a given visit if Q1 = missing and no positive hours recorded under Q2 and Q4.
- If a subject is UNEMPLOYED or employment status is missing, then S1, S2, and S3 will be set to missing.
- If Q2 = 0 and Q4 = 0 or missing then Q2/(Q2 + Q4) = missing (i.e., S1 = missing).
- If Q2 = 0 and Q4 = 0, then set S3 to missing.
- If Q2 is missing or Q4 is missing, then set S1 and S3 to missing.
- If Q4 = missing, then DO NOT set Q5 = missing.
- If Q5 is missing, then apply the following rules:
 - \circ If Q2 > 0, Q4 = 0, and Q5 = missing, then S3 = 100%.
 - \circ If Q2 = 0, Q4 > 0, and Q5 = missing, then S3 is missing.
 - \circ If Q2 > 0, Q4 > 0, and Q5 = missing, then S3 is missing.
- Determine if a subject missed work (based on Q2) in order to analyze the proportion of subjects who missed work:
 - Create a binary (YES or NO) "missed work" variable.
 - A subject will be considered as yes to missed work if Q2 is greater than 0.
 - If Q2 = missing, then MISSED WORK = missing.
 - \circ If Q2 > 0, then MISSED WORK = YES
 - \circ If Q2 = 0, then MISSED WORK = NO

• Therefore, the proportion of subjects who missed work will be counted based on the number of subjects with MISSED WORK = YES.

Partial Study Dates: If the day and/or month are missing, the following conventions will be used to impute the missing visit (or assessment) dates other than the dosing dates:

- 01 for missing start day,
- End of month for missing end day,
- January 1st will be used for a missing start month,
- December 31st for missing end month.

[figure not shown]
In case of partially missing AE start and stop dates, the dates will be imputed by comparing to first dose date of study medication so that the corresponding AEs will be made treatment-emergent whenever possible.

In case of missing or partially missing study drug dosing dates, the dates will not be imputed. Subjects will be considered as not receiving dose on that date.

Rounding

Rounding will be performed only for presentation of results. No rounding will be performed before or during analyses/calculations. The ROUND function of SAS will be used to round results for presentation.

The mean and median will be rounded for presentation to one decimal more than the data were entered into the database. For example, mean systolic blood pressure will be presented to one decimal place (125.2 mmHg) when it is recorded to integer level in the database (110 mmHg). The standard deviation will be rounded to two decimal places more than the data were entered into the database (e.g., 25.31 mmHg for systolic blood pressure). The minimum and maximum values will be presented as entered into the database.

Probabilities will be rounded to three decimal places before assignment of statistical significance and will be presented in rounded format. Probabilities that round to zero or are reported by SAS as zero will be presented as '< 0.001.'

Percentages will be rounded for presentation to one decimal place; e.g., the proportion 0.1244 will be reported in percent as 12.4%.

Score Definitions

1. Mayo Score and Component Scores

 Table 1.
 Definition of Mayo Score and Component Scores

Term	Definition	
Mayo Score	Composite score of UC disease activity based on the subscores of stool frequency $(0-3)$, rectal bleeding $(0-3)$, physician's global assessment $(0-3)$ and endoscopic subscore $(0-3)$. This score ranges from $0-12$ points with higher scores representing more severe disease.	
Partial Mayo Score	Composite score of UC disease activity based on the subscores of stool frequency, rectal bleeding, and physician's global assessment and DOES NOT include the endoscopic subscore. This score ranges from 0 – 9 points with higher scores representing more severe disease.	
9 point Mayo Score (without PGA)	Composite score of UC disease activity based on the subscores of stool frequency $(0-3)$, rectal bleeding $(0-3)$, and endoscopic subscore $(0-3)$. This score ranges from $0-9$ points with higher scores representing more severe disease.	
6 point Mayo Score (without PGA and endoscopy subscore)	Composite score of UC disease activity based on the subscores of stool frequency $(0-3)$ and rectal bleeding $(0-3)$. This score ranges from $0-6$ points with higher scores representing more severe disease.	

[figure not shown]

Table 2. Definition of Endpoints Based on Mayo Score and Component Scores

Term	Definition
Clinical remission per Partial Mayo Score	PMS ≤ 2 and no individual subscore ≥ 1
Clinical response per Partial Mayo Score	Decrease in PMS \geq 2 points and \geq 30% from Study M11-290-Baseline
Clinical remission per Mayo Score	Mayo score ≤ 2 and no individual subscore > 1
Clinical response per Mayo Score	Decrease in Mayo Score \geq 3 points and \geq 30% from Study M11-290-Baseline
Mucosal healing	Endoscopy subscore of 0 or 1
Clinical remission per 9 point Mayo Score (without PGA)	Defined as the 9 point Mayo Score (without PGA) \leq 2 and no individual subscore $>$ 1
Clinical remission per 6 point Mayo Score (without PGA and endoscopy subscore)	Defined as the 6 point Mayo Score (without PGA and endoscopy subscore) ≤ 1

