During the Study Drug Dosing Period, a subject with confirmed (viral test positive) or suspected COVID-19 infection can only be dosed with study drug if the following COVID-19 viral clearance criteria are met:

- Symptomatic subjects: At least 2 negative viral tests in a row, ≥ 24 hours apart after at least 10 days have passed since recovery, defined as resolution of fever without use of antipyretics and improvement in respiratory symptoms (e.g., cough, shortness of breath)
- Asymptomatic subjects: At least 2 negative viral tests in a row, ≥ 24 hours apart after at least 10 days have passed since prior positive result (note: subjects who develop symptoms will follow guidance above for symptomatic subjects)

Delays in study drug dosing due to the above COVID-19 testing guidance for subjects must be discussed with the AbbVie medical contact, along with the possibility of premature discontinuation from the study drug dosing period. Frequency or timing of COVID-19 testing and intervals between testing for the above viral clearance criteria may

be adjusted to account for epidemiologic trends, updated information regarding infectivity, and local/institutional guidelines.

If, during the course of study drug administration, the subject prematurely discontinues study drug use, the procedures outlined for the Termination Visit must be completed within 2 weeks of the last dose of study drug, and preferably prior to the initiation of another therapy. However, these procedures should not interfere with the initiation of any new treatments or therapeutic modalities that the Investigator feels are necessary to treat the subject's condition. Following discontinuation of the study drug, the subject will be treated in accordance with the Investigator's best clinical judgment.

[figure not shown]
A final phone call will be made to the subject at least 70 days after the last dose of study drug to determine the status of any ongoing AEs/SAEs or the occurrence of any new AEs/SAEs.

All attempts must be made to determine the date of the last dose of study drug and the primary reason for premature discontinuation. The information will be recorded on the appropriate eCRF page.

For subjects that are considered lost to follow-up, reasonable attempts must be made to obtain information on the final status of the subject. At a minimum, two phone calls must be made and one certified letter must be sent.

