9.0 Study Drug Exposure and Compliance

The duration (days) of study drug exposure and treatment compliance (%) will be summarized using descriptive statistics.

Study drug exposure will be calculated as follows:

ADA exposure in Study M10-870 = last dose date of ADA in Study M10-870 – first dose date of ADA in Study M10-870 + 14 days

Overall ADA exposure in Study M11-290 & Study M10-870 = ADA exposure in Study M10-870 + Overall ADA exposure in Study M11-290 (see Study M11-290 SAP)

Treatment compliance (%) is defined as the number of study drug injections received divided by the number of injections planned.

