11.4 Analysis of Vital Signs and Weight

The following vital sign parameters will be obtained at each visit and summarized:

- Sitting systolic blood pressure (mmHg)
- Sitting diastolic blood pressure (mmHg)
- Sitting heart rate (or pulse) (bpm)
- Weight (kg)
- Height (cm)
- Body Mass Index (kg/m²)
- Respiratory rate (rpm)
- Body temperature (°C)

For continuous vital sign parameters, mean change from Baseline to minimum (smallest) value, maximum (largest) value, and final value during ADA exposure in Study M10-870 will be summarized. Subjects with potentially clinically significant results during ADA exposure in Study M10-870 will be identified according to the criteria in Table 3. Vital sign results meeting the criteria for potentially clinically significant findings will also be identified in a listing.

[figure not shown]

Table 3. Criteria for Potentially Clinically Significant Vital Sign Results

[figure not shown]
Vital Sign	Criterion	Definition of Potentially Clinically Significant
Systolic blood pressure	Low	Value ≤ 70 mmHg and decreased ≥ 20 mmHg from initial value
	High	Value $\geq 160 \text{ mmHg}$ and increased $\geq 20 \text{ mmHg}$ from initial value
Diastolic blood pressure	Low	Value \leq 50 mmHg and decreased \geq 15 mmHg from initial value
	High	Value ≥ 105 mmHg and increased ≥ 15 mmHg from initial value
Pulse	Low	Value \leq 50 bpm and decreased \geq 30 bpm from initial value
	High	Value ≥ 120 bpm and increased ≥ 30 bpm from initial value

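### The SAP does not restrict efficacy values by treatment status, so a Termination Visit score taken after another UC therapy has started can count as response on adalimumab and be carried forward by LOCF

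*SAP*

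**What the plan says.** **Timing of the last assessment.** Protocol 5.4.1 says that, after premature discontinuation, the Termination Visit procedures "must be completed within 2 weeks of the last dose of study drug, and preferably prior to the initiation of another therapy". The same paragraph adds that these procedures must not hold up any treatment the investigator considers necessary. Protocol Table 1 schedules PMS and PUCAI at the Week 288/Premature Discontinuation visit.

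**How efficacy values are chosen.** SAP 6.0 defines analysis windows by days from the first dose and takes the assessment nearest the nominal day. For LOCF it excludes only baseline and pre-baseline values and then states: "Missing values after baseline will be imputed using the last non-missing values after baseline and prior to the missing value". SAP 10.1 applies observed cases (OC) and LOCF to the efficacy endpoints. SAP 10.4 leaves sensitivity analyses open.

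**Where treatment status is used.** For laboratory data SAP 6.0 has a separate definition: "Final evaluation during ADA exposure in Study M10-870 (for laboratory analyses): the last non-missing observation collected in the study within the ADA exposure window". SAP 11.4 does the same for vital signs, where the "final value during ADA exposure in Study M10-870 will be summarized". SAP 9.0 computes exposure as last dose date minus "first dose date of ADA in Study M10-870 + 14 days". The general definition, "Final evaluation during the study: the last non-missing observation collected in the study after the first dose of study drug", has no such limit.

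**The concern.** The stated objective includes maintenance of clinical response under repeated adalimumab. Subjects with persistently uncontrolled disease are to be discontinued, so treatment failures pass through the Termination Visit, and they are the subjects most likely to need another drug quickly. If that drug starts first, PMS and PUCAI may partly reflect it. Nothing in the SAP stops such a score from entering the adalimumab response or remission rate.

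Under LOCF the effect does not stay at one visit: the score stands in for the subject at every later visit. By-visit proportions with 95% confidence intervals are the main efficacy output. Under Protocol 8.1.7 and SAP 4.4 they also feed an interim report for regulatory submission.

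**Working it through.** The plan states no figure on this point that could be reproduced, so the check traces one score through the rules and then sizes it.

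**1. Can a post-switch score exist?** Yes. Protocol 5.4.1 makes assessment before new therapy a preference and forbids delaying treatment for it. PMS and PUCAI are due at that visit.

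**2. Does any SAP rule remove it?** No.
- Windows (SAP 6.0) depend only on days since first dose.
- OC uses any observed value selected in its window.
- LOCF bars only baseline and pre-baseline values.
- No rule censors efficacy values, or sets them to non-response, after the last dose or after another UC therapy starts.

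**3. How many visits can one score fill?** The SAP 6.0 window table has 19 post-baseline visits: Weeks 4, 8 and 12; then 24 to 120 in steps of 12 (9 visits); then 144 to 288 in steps of 24 (7 visits). 3 + 9 + 7 = 19.

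| Termination Visit at Rx Day | Window | Later visits filled by LOCF |
|---|---|---|
| 100 | Week 12 | 16 |
| 200 | Week 24 | 15 |
| 350 | Week 48 | 13 |
| 700 | Week 96 | 9 |

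**4. Size per subject.** SAP 4.3 expects 55 subjects outside Japan, so one subject in a LOCF table is 1/55 = 1.8 points. The number affected is not in the documents. As an assumed range:
- 2 subjects: 2/55 = 3.6 points
- 3 subjects: 3/55 = 5.5 points
- 5 subjects: 5/55 = 9.1 points

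As an illustration with exact 95% intervals, 28/55 = 50.9% (37.1 to 64.6) becomes 26/55 = 47.3% (33.7 to 61.2) if 2 are reclassified, and 23/55 = 41.8% (28.7 to 55.9) if 5 are.

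**5. Would the existing exposure window solve it?** Largely not. The window ends about 14 days after the last dose (SAP 9.0), and the Termination Visit is due within 2 weeks of it (Protocol 5.4.1). The limits nearly coincide, so an on-time post-switch score would stay in and only late visits would drop out.

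**6. Would discarding the post-switch score solve it?** No. Take a subject in remission at Week 48 who flares, switches, and still has active disease at a Termination Visit in the Week 60 window. Under the present rules, failure is recorded at Week 60 and carried on. If the score were simply discarded, LOCF would carry the Week 48 remission to all 13 later visits. The rule must therefore set non-response from the switch onward.

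**The case against.** Several counter-arguments have force.

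- **Direction and size are not demonstrated.** A reader might infer that remission is overstated by 5.5 to 9.1 points. The documents do not support that. The 3 to 5 subjects behind those figures are assumed, and the figures also require every one of them to be wrongly classed as a responder and never assessed again. A post-switch score counts only if it meets the threshold and is the value selected in its window. PMS diary items average 5 days taken from up to 14, so flare days before the switch may still be included.
- **The contrast with safety data is not an inconsistency in itself.** A reader might infer that the SAP contradicts itself by limiting laboratory and vital-sign values to exposure but not efficacy. Those limits can serve safety attribution, and using all observed data in all treated subjects fits the protocol's ITT population. The general final-value definition is also not cited in SAP 10. The operative text is the window and LOCF rules.
- **Part of the harm comes from by-visit LOCF.** Protocol 8.1.4 plans observed data and non-responder imputation by visit, with LOCF only as an added last-visit summary. Reconciling the SAP to that would remove the by-visit carry-forward. It would not remove the post-switch score at its own visit, because that value is not missing, nor from the last-visit LOCF.
- **The study is descriptive.** No type I error or power figure is affected, OC is shown beside LOCF, and interim imputation stops at the time point a subject could have reached.

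These points limit the size and certainty of the problem. None supplies the missing rule.

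**Conclusion.** The gap is real and its size is unknown. As written, a PMS or PUCAI score obtained after another UC therapy has started can be counted as response or remission on adalimumab. It can then be carried to up to 15 of 19 visits from Week 24, or 13 of 19 from Week 48, at 1.8 points per subject with 55 subjects in the LOCF denominator.

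This rests on three conditions: the new therapy precedes the Termination Visit, the score meets the threshold, and the score is the one selected in its window. If a scheduled value lies nearer the nominal day, the SAP does not say whether LOCF carries the selected value or the chronologically last one. Overstated response is the plausible direction but is not shown. The change is worth making because it is specific and cheap, not because a material bias has been established.

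**What to change.** In SAP 6.0 and 10.1:

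1. Flag the start date of any replacement UC therapy. Limit the flag to the UC-directed agents in Protocol 5.2.3.3: biologics with a potential UC effect, tofacitinib, systemic cyclosporine, tacrolimus or mycophenolate, intravenous corticosteroids, and investigational UC drugs. Leave out live vaccines and other non-UC products on that list.
2. For subjects who discontinue adalimumab, set binary efficacy endpoints to non-response at the first post-switch visit and at all later visits, so that an earlier response is not carried past the switch. In the OC table this affects only assessments actually made.
3. For continuous endpoints, set post-switch values to missing. State that LOCF then carries the last pre-switch value.
4. For subjects who resume adalimumab after a prohibited medication, which Protocol 6.3 foresees, keep later on-drug assessments.
5. Footnote the number of assessments affected and show the unrestricted summary as a sensitivity analysis.

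Extending the 14-day exposure window to efficacy is optional and would remove only late Termination Visits. If it is used, correct the SAP 6.0 cross-reference to Section 9.1: the exposure formula stands in 9.0 and there is no 9.1.

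The cost is SAP wording and one derivation. Last-dose and concomitant-medication dates are already collected, including at the discontinuation visit. Response and remission rates may come out slightly less favourable. Nothing in clinical management changes.
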